## 3.5.3. Trial Stopping Rules

The trial can be prematurely terminated by the DSMB or Sponsor for any of the following reasons:

• Occurrence of two SBP-9330-related SAEs in a cohort

Altasciences Project Number: CNO-P5-319

• Occurrence of one death attributable to the study treatment

Altasciences Project Number: CNO-P5-319

#### 4. SUBJECT POPULATION

Subjects meeting all the inclusion criteria and none of the exclusion criteria at Screening may be eligible for participation in this study. Continued eligibility will be assessed upon admission to the CRU, prior to the first study drug administration.

Screen failures are defined as participants who consent to participate in the clinical trial but are not subsequently randomly assigned to the study intervention or entered in the study.

An effort will be made to include similar proportions of males and females in the study.

#### 4.1. Inclusion Criteria

- 1. Provision of written informed consent prior to the initiation of any protocol-specific procedures
- 2. Stated willingness to comply with all study procedures and availability for the duration of the study
- 3. Healthy male or female subject  $\geq 18$  and  $\leq 55$  years of age
- 4. Body mass index (BMI)  $\geq 18.5 \text{ kg/m}^2$  and  $\leq 32.0 \text{ kg/m}^2$
- 5. Body weight  $\geq$  50.0 kg at Screening
- 6. A female subject must meet at least one of the following criteria:
  - a) Is of childbearing potential and agrees to use an acceptable contraceptive method. Acceptable contraceptive methods include:
    - Total abstinence, in accordance with the lifestyle of the subject, from at least 30 days prior to the first study drug administration through to at least 90 days after the last dose of the study drug
    - One of the following contraceptive methods, used in combination with a barrier method (e.g., a diaphragm, a cervical cap, or a condom), from at least 30 days prior to the first study drug administration through to at least 90 days after the last dose of the study drug:
      - Intrauterine device (with or without hormones)
      - Spermicide

Or

- b) Is of non-childbearing potential, defined as surgically sterile (i.e., has undergone complete hysterectomy, bilateral oophorectomy, or tubal ligation) or is in a postmenopausal state (i.e., at least 1 year without menses prior to the first study drug administration without an alternative medical condition and confirmed with a serum follicle-stimulating hormone [FSH] > 40 IU/L at Screening)
- 7. Male subjects, if not surgically sterilized, must agree to use adequate contraception and not donate sperm from the first admission to the CRU until 90 days after the last study drug administration. Adequate contraception for the male subject (and/or his female partner) includes the following:

Altasciences Project Number: CNO-P5-319

- Use of spermicide, hormonal contraceptives or an intrauterine device combined with at least one of the following forms of contraception: a diaphragm, a cervical cap, or a condom
- Double-barrier method

Total abstinence, in accordance with the lifestyle of the subject, from at least 30 days prior to the first study drug administration until 90 days after the last study drug administration, is also acceptable

- 8. **Parts A and B only:** Never- or nonsmoker (a nonsmoker is defined as someone who completely stopped using nicotine products for at least 2 years prior to the first study drug administration)
- 9. Have no clinically significant medical or mental health conditions captured in the medical history or evidence of clinically significant findings on the physical examination and/or ECG, as determined by an Investigator
- 10. No clinically significant abnormalities in blood pressure, heart rate, body temperature and respiratory rate and no evidence of orthostatic hypotension or postural tachycardia at Screening as defined below:
  - a)  $100 \text{ mmHg} \le \text{systolic blood pressure (BP)} \le 140 \text{ mmHg in supine position.}$
  - b) 60 mmHg  $\leq$  diastolic BP  $\leq$  90 mmHg in supine position.
  - c) 60 beats per minute (bpm)  $\leq$  heart rate  $\leq$  100 bpm in supine position.
  - d)  $35.5 \, ^{\circ}\text{C} \leq \text{body temperature} \leq 37.5 \, ^{\circ}\text{C}$ .
  - e) 10 breaths per minute  $\leq$  respiratory rate  $\leq$  22 breaths per minute.
  - f)  $\geq$  20 mmHg decrease in systolic BP from supine to standing.
  - g)  $\geq 10$  mmHg decrease in diastolic BP from supine to standing.
  - h)  $\geq$  30 bpm increase in heart rate from supine to standing.

## Part C Only:

- 11. Are current tobacco cigarette smokers who smoke an average of 10 or more cigarettes per day in the 30 days prior to Screening
- 12. Expired breath CO level ≥10 parts per million (ppm) at Screening and prior to the first study drug administration
- 13. Positive test result for cotinine at Screening and prior to the first study drug administration
- 14. Are not motivated to try to quit smoking from Screening and through 30 days from the first study drug administration

## 4.2. Exclusion Criteria

- 1. Female who is lactating
- 2. Female who is pregnant according to the pregnancy test at Screening or prior to the first study drug administration

Altasciences Project Number: CNO-P5-319

- 3. Female who is planning to become pregnant during this study or within 90 days after the last study drug administration
- 4. Male with female partner who is pregnant, lactating, or planning to become pregnant during this study or within 90 days after the last study drug administration
- 5. Poor venous access as determined by an Investigator at Screening
- 6. History of significant hypersensitivity to SBP-9330 or any related products (including excipients of the formulations) as well as severe hypersensitivity reactions (like angioedema) to any drugs
- 7. Presence of any medical condition that, in the opinion of an Investigator, poses an unacceptable risk to the subjects
- 8. Presence or history of significant gastrointestinal, liver or kidney disease, or surgery that may affect drug absorption
- 9. Evidence or history of clinically significant cardiovascular, pulmonary, hematologic, psychiatric (including mood and substance use disorders), neurological (including migraines, seizures, and epilepsy), endocrine, renal, hepatic, gastrointestinal, immunologic or dermatologic disease
- 10. History of malignancy within the past five years, except for successfully treated basal cell carcinoma of the skin
- 11. History of suicidal ideation or suicidal behaviour as per the C-SSRS questionnaire administered at Screening
- 12. Evidence or history of significant psychiatric disease or any DSM-5 disorder as assessed by the Mini International Neuropsychiatric Interview (M.I.N.I.) administered at Screening
- 13. Routine or chronic use of more than three grams of acetaminophen daily
- 14. Strenuous activity, sunbathing, and contact sports within 48 hours prior to (first) admission to the CRU
- 15. Current alcohol consumption exceeding two standard drinks per day on average (1 standard drink=10 grams of alcohol) for male subjects and one standard drink per day on average for female subjects
- 16. History of alcohol or drug (other than caffeine) use disorder within 12 months prior to Screening
- 17. Any clinically significant illness in the 28 days prior to the first study drug administration
- 18. QTcF interval (QT interval corrected for heart rate according to Fridericia) > 450 ms for males and > 470 ms for females at Screening or on Day -1
- 19. Parts A and B only: Positive test result for alcohol and/or drugs of abuse at Screening or prior to the first drug administration
- 20. Positive test results for HIV-1/HIV-2 antibodies, hepatitis B surface antigen (HBsAg) or hepatitis C antibody (HCVAb)

Altasciences Project Number: CNO-P5-319

- 21. Consumption of any prescription drugs (with the exception of hormonal contraceptives or hormone replacement therapy) or over-the-counter (OTC) medications and nutrients known to modulate cytochrome P450 (CYP450) enzymes activity (e.g., grapefruit or grapefruit juice, pomelo juice, star fruit, or Seville [blood] orange products) or St. John's Wort within 14 days prior to the first study drug administration
- 22. Consumption of other prescription and over-the-counter medication not specifically excluded by Exclusion Criterion 21 including health supplements and herbal remedies within 7 days prior to the first study drug administration (an exception is made for paracetamol [acetaminophen], which is allowed up to admission to the clinic).
- 23. Any other clinically significant abnormalities in laboratory test results at Screening that would, in the opinion of an Investigator, increase the subject's risk of participation, jeopardize complete participation in the study, or compromise interpretation of study data
- 24. Intake of an investigational product in the 30 days or 5 half-lives (whichever is longer) prior to Screening
- 25. Inclusion in a previous cohort of this clinical study
- 26. Employee of the contract research organization (CRO) or the Sponsor.
- 27. Blood donation (excluding plasma donation) of approximately 500 mL within 56 days prior to Screening
- 28. Plasma donation within 7 days prior to Screening

#### Part C Only:

- 29. History of generalized rash reaction to any drugs
- 30. Positive test result (except cotinine) for alcohol and/or drugs of abuse at Screening or prior to the first study drug administration
- 31. Use of smoking cessation aids (NRT, bupropion, or varenicline) within 30 days prior to the first study drug administration
- 32. Unable to abstain from smoking tobacco cigarettes for at least 1 hour before and 2 hours after study drug administration
- 33. Unable to abstain from using nicotine-containing products other than tobacco cigarettes (e.g., pipes, cigars, e-cigarettes or vapes, nicotine topical patches, nicotine gum, or nicotine lozenges) during the study

#### 4.3. Withdrawal Criteria

#### 4.3.1. Before First Treatment Administration

Before the first treatment administration, continuing to meet the study inclusion/exclusion criteria will govern which subjects are randomized to treatment. Subjects withdrawn before first treatment administration will not be followed up and will not undergo EOS/Follow-up assessments. Other safety assessments may be performed if required.

Altasciences Project Number: CNO-P5-319

Subjects are free to withdraw their consent to participate in the study at any time, without prejudice. The reason for their withdrawal or for deciding to end their participation will be documented.

#### 4.3.2. After First Treatment Administration

Subjects may, at any time, voluntarily withdraw from the study or be removed from the study at the discretion of an Investigator or Sponsor. An Investigator may withdraw a subject at any time if it is determined that continuing the study would result in a significant safety risk to the subject or if their behavior is deleterious to the study environment.

If such withdrawal occurs, or if the subject fails to return for visits, an Investigator should determine the primary reason for a subject's premature withdrawal from the study and record the reason in the subject's study documents.

An Investigator may remove a subject from the study on the recommendation of the PK facility and/or Sponsor due to an unanticipated event that could result in an inadequately characterized PK profile, such as a missed blood draw, an AE, meal deviation or concomitant medication intake.

Attempts should be made to have such subjects complete the EOS/Follow-up assessments. The EOS/Follow-up assessments should be performed as soon as possible after the last study treatment administration.

The blind may be broken only in emergency situations, where knowledge of the treatment that the subject received is necessary for safety management (Section 5.2.4).

Details of reasons for removal of subjects will be recorded, reported to the Sponsor and documented in the clinical study report.

For subjects lost to follow-up (i.e., those subjects whose status is unclear because they fail to appear for study visits without stating an intention to withdraw), an investigator should show "due diligence" by documenting in the source documents steps taken to contact the subject, e.g., dates of telephone calls, registered letters, etc.

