### 4.5. Concomitant Treatment

Except for medication which may be required to treat AEs, no other treatment or medication other than the study drugs will be allowed from the first dosing until all study activities and evaluations have been completed.

Systemic contraceptives and hormone replacement therapy are permitted for female subjects as per Section 4.1.

Subjects will be instructed to notify the CRU about any new medications taken after the start of the study treatment. All medications and significant non-drug therapies (including physical therapy and blood transfusions) administered after the subject has received the study treatment must be listed in the subject case report form (CRF). The drug name and dose taken will be noted. An investigator or delegate and/or the Sponsor will decide whether the subject will be permitted to remain in the study, depending on the drug used, the time of drug intake, etc.

Subjects receiving the COVID-19 vaccine should be fully vaccinated at least 14 days prior to receiving Investigational Product.

Altasciences Project Number: CNO-P5-319

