## 5.2.3. Method of Assigning Subjects to Treatment Groups

The CRU will generate the randomization code for each cohort with a computer program according to the study design, the number of subjects and the treatment to be administered. Once generated, the randomization code will be final and will not be modified.

Subjects enrolled in the SAD sentinel groups will be randomized 1:1 to receive SBP-9330 or matching placebo while the rest of the subjects in the cohort will be randomized 5:1 to receive SBP-9330 or matching placebo. Subjects enrolled in the MAD and Smoker cohorts will be randomized 8:2 to receive SBP-9330 or matching placebo.

Subjects who sign the informed consent form (ICF) and are randomized but do not receive the study treatment may be replaced. Subjects who sign the ICF, are randomized and received at least 1 dose of the study treatment, and are withdrawn prematurely from the study, may be replaced by an equal number of newly enrolled subjects. A new unique randomization number

Altasciences Project Number: CNO-P5-319

will be assigned to the replacement subject. The replacement list will be provided and will be identical to the original randomization scheme.

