4 ANALYSIS POPULATIONS

- **Safety population:** The safety population will include all subjects who received at least 1 dose of one of either the SBP-9330 or placebo.

The number of subjects who were included, who discontinued, and who completed the study will be tabulated. The primary reasons for discontinuation will be provided.

- **Pharmacokinetic Population:** The PK population will include all subjects who have received at least 1 dose of SBP-9330 and have at least 1 PK concentration after dosing.

Subjects who do not complete the sampling schedule of one or more study days may be included in the PK and statistical populations for only the PK parameters that are judged not to be affected by the missing sample(s).

Subjects with protocol deviations or adverse events (e.g., vomiting) that could be considered to have an impact on the PK results may be excluded from the PK population. Excluded subjects will be tabulated with the exclusion reason in the PK listings.

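### Protocol 4.3.2 allows removal from the whole study when an AE may spoil the PK profile, and its loose end-of-study wording can cut planned safety observation short in such subjects

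*Protocol*

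**What the plan says.** **Removal.** Protocol Section 4.3.2 states: "An Investigator may remove a subject from the study on the recommendation of the PK facility and/or Sponsor". The ground is an unanticipated event that could give an "inadequately characterized PK profile, such as a missed blood draw, an AE, meal deviation or concomitant medication intake". Significant safety risk is a separate ground in the same section, so this clause serves PK quality.

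**Medication.** Section 4.5 says: "Except for medication which may be required to treat AEs, no other treatment or medication other than the study drugs will be allowed". Systemic contraceptives and hormone replacement are also permitted. After a medication is taken, the choice lies with the investigator (or a delegate), the Sponsor, or both, who "will decide whether the subject will be permitted to remain in the study, depending on the drug used, the time of drug intake, etc".

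**Replacement.** Under Section 5.2.3, dosed subjects who "are withdrawn prematurely from the study, may be replaced by an equal number of newly enrolled subjects".

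**Follow-up after removal.** Section 4.3.2 adds: "Attempts should be made to have such subjects complete the EOS/Follow-up assessments". On timing: "The EOS/Follow-up assessments should be performed as soon as possible after the last study treatment administration". Section 3.3, by contrast, obliges early terminators to complete the EOS procedures, as do the Synopsis for Parts B and C and SAP Section 3.1. Section 7.4 ends AE monitoring at the Follow-up Visit.

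**Analysis.** SAP Section 4 provides that subjects with deviations or AEs "that could be considered to have an impact on the PK results may be excluded from the PK population". It also lets subjects with incomplete sampling contribute the parameters that are unaffected.

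**The concern.** A secondary objective is given a route to end collection of data for the primary one. The events that open this route include an AE. Concomitant medication is also listed and, under Section 4.5, medication taken after dosing will mostly be treatment for an AE. The subjects who may leave early are therefore selected on the outcome of main interest.

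For them, Section 4.3.2 both weakens the EOS visit (attempts only) and brings it forward. An early EOS closes the window in which new AEs are routinely captured and drops the scheduled laboratory tests, ECGs, vital signs and C-SSRS that lie beyond it. Delayed emergence of significant AEs is one of the things that must be acceptable before escalation under Section 3.5, so late events matter here. The AE summaries in SAP Section 8 are numbers and percentages of subjects, with no adjustment for observation time, and SAP Section 9.4 rules out imputation. Nothing planned corrects for shortened observation.

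**Working it through.** No sample size, power or alpha figure bears on this point. Protocol Section 8.7 says the sample size has no statistical basis. The check sets the sections side by side and then does the day arithmetic.

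**1. Do the sections agree on what follows removal?**

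- Section 4.3.2: EOS is to be attempted, at the earliest opportunity after the last dose.
- Section 3.3: EOS is compulsory for early terminators.
- Tables 1 to 3, footnotes: early discontinuers should complete EOS.

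These are three strengths of obligation for the same visit, and only Section 4.3.2 ties its timing to the last dose.

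**2. Is removal from the study needed to protect PK?** SAP Section 4 covers the same kinds of event (AEs, protocol deviations, missing samples) by excluding the subject or limiting the parameters used. PK quality is protected without ending safety observation.

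**3. Planned time from last dose to EOS** (Protocol Sections 3.3.1 to 3.3.3)

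- Part A single-dose cohorts: Day 8 − Day 1 = 7 days (6 to 8 with the ±1 day window).
- Parts B and C: Day 21 − Day 14 = 7 days (6 to 8).

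Read literally, the Section 4.3.2 timing allows this to fall to near 0.

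**4. Scheduled observation lost.** Assumption: EOS is done on the day of removal, day *d*. The documents do not fix that day.

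Parts B and C: lost = 21 − *d*, out of 21 − 1 = 20 planned days from first dose.

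| *d* | Days lost | Share of 20 |
|---|---|---|
| 3 | 18 | 90% |
| 7 | 14 | 70% |
| 10 | 11 | 55% |
| 14 | 7 | 35% |

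Part A single-dose cohorts: lost = 8 − *d*, giving 7, 6 or 5 days for *d* = 1, 2 or 3.

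**5. Does replacement dilute the AE rate?** Let *X* ~ Bin(*n*, *p*) be the active subjects with an AE. Suppose all are removed and replaced once, and the replacements have AEs at the same rate. All dosed subjects count in the Safety population, so the expected crude incidence is E[*X*(1 + *p*)/(*n* + *X*)]. The AE rates are assumed.

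| True rate | *n* = 8 active | *n* = 6 active |
|---|---|---|
| 10% | 9.1% | 8.9% |
| 25% | 23.5% | 23.0% |
| 40% | 38.4% | 37.9% |

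Even in this extreme case the dilution is about 1 to 2 percentage points.

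**6. If the planned safety visits were kept after a PK-driven removal**, the 7-day window would stand in Part A and observation would run to Day 21±1 in Parts B and C. No scheduled observation would be lost for a PK reason.

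**The case against.** The strongest reply is that the clause only says an Investigator may act, and that the protocol already guards the primary data. Much of this stands:

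- A removed subject stays in the Safety population (Section 8.1.1), and the AE that led to removal still counts in incidence and severity.
- TEAEs leading to withdrawal have their own summary (SAP Table 8).
- Section 7.4 requires unresolved AEs to be followed past the last visit, and Section 3.5.2 requires serial follow-up of severe AEs.
- The DSMB reviews all subjects in a cohort (Section 3.2), so recorded AEs are not hidden from it.
- Section 4.5 itself gives discretion over staying in the study after medication. SAP Section 4 governs analysis only, so it does not contradict Section 4.3.2.
- Section 3.5.1 already holds the next dose after a confirmed drug-related moderate or severe AE pending review. Some lost dosing days would therefore arise without the PK clause.

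These protections do not cover an event that has not yet appeared at an early EOS, or scheduled assessments no longer made. The mismatch with Section 3.3 also remains.

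Two stronger readings are tempting. A reader might infer that the rule falls on the active arm alone and so reveals treatment, because only active subjects have an SBP-9330 profile. The documents do not support this. The named triggers can be seen at the site in either arm, and Section 5.2.4 has interim concentrations relabelled with alternative subject numbers before they reach the PK facility and Sponsor. A reader might also infer that replacement makes the drug look materially safer. Step 5 shows the effect is small.

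**Conclusion.** The point holds as a gap in wording that can cost primary safety data. Section 4.3.2 permits removal from the whole study, for a PK reason, in subjects who may have been selected by an AE. It then asks less of their EOS visit than Section 3.3 does.

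At most, the 7 days from last dose to EOS shrink to near 0, and a Day 3 removal in Parts B or C loses 18 of 20 planned days. Both are upper bounds: they assume that the discretion is used and that EOS falls at once. The documents do not say how often either would happen. The loss is confined to new or delayed events and scheduled assessments. It would be wrong to conclude that safety follow-up necessarily stops, or that AEs already seen leave the analysis. No sample-size figure is affected. This is a cheap improvement worth making, not a flaw that undermines the design.

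**What to change.** Reconcile Protocol Sections 3.3, 4.3.2, 4.5, 5.2.3 and 7.4 with SAP Section 4 so that two matters are kept apart:

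- A compromised PK profile is handled by excluding the affected samples, parameters or subject from the PK analysis under SAP Section 4.
- The end of safety follow-up is governed separately. Subjects whose PK is compromised keep the planned safety and EOS assessments, even if an additional subject is enrolled for PK.

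State the EOS obligation and its timing once, in the same terms in Sections 3.3 and 4.3.2 and the footnotes to Tables 1 to 3. Decisions on dosing and withdrawal stay with the existing safety rules; nothing is proposed on them here.

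The cost is about one paragraph of protocol wording plus consistent cross-references. The downside is that a few subjects will contribute safety data without usable PK.
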